HRPO Protocol

1) Protocol Title (Version # and/or Version Date)

The Emotions and Decisions of Couples, #12-433, v. 06/13/2018

2) IRB Review History

N/A

3) Objectives

The proposed study is an experimental comparison of the effects of alcohol on arousal and emotion-regulation between 112 Distressed Violent (DV) and 112 Distressed Nonviolent (DNV) partners. One partner from each DV couple will be pseudo-randomly selected and yoked to a DNV partner of the same sex and a relationship satisfaction within a five-point range for participation in the experiment. To test the overall hypothesis that over-arousal is a mechanism through which alcohol is associated with increases in the frequency and severity of IPV, the selected partners will participate in a counter-balanced placebo session and alcohol administration session during which EEG, psychophysiology and pupillary response measurements of arousal will be collected during an emotion regulation task.

Specific Aim 1: To determine if normal increases in arousal after alcohol exposure is potentiated by evocative partner stimuli is greater for distressed violent (DV) partners compared to distressed nonviolent (DNV) partners. *Hypothesis 1a:* DV and DNV partners will experience comparable alcohol related increases in arousal. *Hypothesis 1b:* DV partners will demonstrate greater arousal increases by evocative partner displays than DNV partners. *Hypothesis 1c:* DV partners will experience greater arousal when exposed to alcohol and evocative partner stimuli than DNV partners.

Specific Aim 2: To determine if alcohol induced arousal interferes with DV partners' ability to regulate emotion in response to evocative partner stimuli compared to DNV partners. *Hypothesis 2a:* Emotion regulation during evocative stimuli will be reduced compared to neutral stimuli. *Hypothesis 2b:* Emotion regulation during evocative stimuli will be reduced by alcohol. *Hypothesis 2c:* DV partners will be less able to regulate emotion during evocative stimuli than DNV partners. *Hypothesis 2d:* Alcohol will interfere with DV partners' ability to regulate emotion during evocative stimuli compared to DNV partners.

4) Background

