DV couples also express higher levels of negative affect, such as contempt and belligerence, which escalate conflict beyond that seen in DNV couples (Gottman et al., 1995). Compared to DNV couples, DV couples become more psychologically abusive, emotionally aggressive and increasingly physiologically aroused as their conflict continues because of these patterns (Babcock et al., 1993; Frye & Karney, 2006; Gottman, et al., 1995; Jacobson, et al., 1994). Furthermore, verbal aggression and physical aggression are highly correlated in couples (Lundeberg, Stith, Penn & Ward, 2004) with 94% of those reporting physical aggression also

reporting verbal aggression (Shook, Gerrity, Jurich & Segrist, 2000). DV couples also have difficulty disengaging from conflict once it begins without escalating to physical aggression due in part to their highly aroused state (Ekman, 1984; Frye & Karney, 2006; Gottman, 1994; Jacobson, et al., 1994; Margolin, John & Foo, 1998; O'Leary, 1999). These findings suggest that DV couples are unable to regulate their emotional responses in the face of evocative conflict. Furthermore, partners in relationships whose conflict chronically generates such arousal become hypervigilant to potentially threatening and escalating interactions, and are more likely to misattribute threat potential to relatively neutral or positive acts (Gottman, 1994). These findings also suggest a sensitization process whereby repeated exposures to aversive dyadic interactions result in a progressive amplification of the arousal response to the partner's behavior.

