Stimuli Acquisition: Video cameras will be focused on the face of each partner to capture the content of the partner's speech as well as the partner's facial expressions during the discussion of a disagreement using two Canon VIXIA HF R400 video cameras. To ensure that there are not experimenter-introduced differences in the evocative stimuli used between groups in the subsequent experimental sessions, and to ensure we choose sufficiently arousing partner displays, stimuli selected will be according to the hierarchy of the Specific Affect (SPAFF) coding system (e.g., contempt, belligerence, criticism, defensiveness, stonewalling, respectively). It is important to note that conflict intensity differences likely naturally exist between DV couples and DNV couples (see Significance). Our method will ensure, however, that there are no experimenter introduced differences in the stimuli selected. Inter-rater reliabilities will be calculated on 50% of the videos and coders retrained to criterion if necessary. DV couples display at least 192 evocative behaviors per 15-minute disagreement discussion,⁶⁷ and partners are roughly equivalent in such displays¹⁸ ensuring ample evocative stimuli for subsequent sessions. Displays of these evocative behaviors also distinguish DNV from satisfied couples.⁴⁰ Partners will be excluded from the remainder of the study should the couple fail to provide sufficient stimuli. If the couple is symmetrical in violent behavior, one partner will be randomly selected to participate in the remaining sessions. If the couple is asymmetrical, the most violent partner will be selected for participation. DV partners will be matched and yoked to a DNV partner of comparable distress.

Emotion-Regulation Sessions: The selected partners (DV, DNV) will return to the laboratory on two separate occasions for the completion of the emotion-regulation sessions of the study. Once participants are prepped for biopotential recording, they will be administered either an alcohol beverage or placebo beverage (counter-balanced alcohol and placebo conditions; see below for procedures).

Alcohol Condition Protocol - Participants will receive a mixed drink (juice and 100-proof vodka) intended to raise their blood alcohol concentration (BAC) to a target dose of 0.08g% using a standard formula for calibrating the alcohol doses to achieve the target BACs.⁶⁸

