
Emotion Regulation Task - The proposed approach for studying emotion regulation has been used in several previous studies,⁶⁹ but we will utilize participant-tailored stimuli (video clips of partner's evocative behavior). During viewing, participants will be instructed to 1) experience the emotion they associate with the video (WATCH), or 2) to suppress the feeling of emotion (DON'T REACT). In the WATCH condition, participants will be instructed to let their

emotional experience occur naturally, and to pay attention to how they feel during the clip. In the DON'T REACT condition, participants will be instructed to attempt to suppress any feelings of emotion so as to prevent an observer watching physiological recordings from knowing that an emotional response has occurred. In both conditions, participants will be asked to indicate their corresponding emotional state using a slider (clicking and dragging with a mouse) on a continuous rating scale anchored by "very negative" (1) and "very positive" (100). A total of 50 unique video clips between 4 and 8 seconds in length will be used in the task; 25 evocative and 25 neutral. Each stimulus will be presented twice: once in the WATCH condition and once in the DON'T REACT condition. On each trial, participants will view a blank screen (1 second), fixation cross (1.5 sec), blank screen (.5 sec), the instruction (WATCH or DON'T REACT; 1.5 sec), the video clip (4-8 sec), and a blank screen (up to 2.5 seconds). The total amount of time required for the task will be approximately 25 minutes. Ratings obtained during the emotion regulation task will be averaged across stimulus type and regulation condition for the placebo and alcohol sessions for statistical analysis.

Participant Remuneration: Each participant will be paid \$20 per hour for their participation in the study. Each partner will have the opportunity to earn \$40 for his/her participation in the *Stimuli Acquisition Session* (\$80 total). The partner invited back for the *Emotion-Regulation Sessions* will have the opportunity to earn \$100 for his/her participation in the *Alcohol beverage Emotion-Regulation Session* and \$20 in the *Placebo beverage Emotion-Regulation Sessions* for a total of \$200 per couple. Participants will receive remuneration in the form of Visa or similar gift cards.

12) List of Appendices

Scale Purpose	Scale Name	Use/Source	α	Population

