Specific Aim 1: To determine if normal increases in arousal after alcohol exposure is potentiated by evocative partner stimuli and is greater for DV partners compared to DNV partners. We will conduct a 2 (beverage condition: alcohol vs. placebo) x 2 (stimulus: evocative vs. neutral) repeated measures ANOVA with a between-subjects factor (partner type: DV vs. DNV). To test whether alcohol increases overall arousal (**Hypothesis 1a**), we will examine the main effect of alcohol vs. placebo on arousal variables, collapsing across partners and stimuli during the WATCH condition as alcohol should effect the arousal of both partner types equally. To test whether DV partners are more aroused by evocative partner displays than DNV partners (**Hypothesis 1b**), we will test the interaction effect of partner type and stimulus type, collapsing across alcohol and placebo conditions. Finally, to test the hypothesis that alcohol induced increases in arousal above placebo will be greater for evocative than neutral stimuli (**Hypothesis 1c**) for DV vs. DNV partners, we will test the three-way interaction in the 2 (DV vs. DNV) x 2 (alcohol vs. placebo) x 2 (evocative vs. neutral) repeated measures ANOVA. Specifically, this contrast will examine the effect of partner type when comparing stimuli type (evocative) to beverage condition (alcohol) on arousal and provides a critical control given that conflict intensity may differ between DV and DNV couples. The 3-way interaction (Hyp1c) will allow us to be able to determine whether the change in arousal between alcohol and placebo sessions for the evocative stimuli differs between couple types. The arousal level of evocative stimuli is matched between alcohol and placebo sessions, thus allowing for a controlled examination of alcohol-induced increases in arousal for evocative stimuli across DV and DNV couples.

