Specific Aim 2: To determine if alcohol induced arousal interferes with DV partners' ability to regulate emotion in response to evocative partner stimuli compared to DNV partners. All hypotheses will be tested using a 2 (beverage condition: alcohol vs. placebo) x 2 (stimulus: evocative vs. neutral) x 2 (regulation condition: WATCH vs. DON'T REACT) repeated measures ANOVA with a between-subjects factor (partner type: DV vs. DNV). Testing specific interactions within the overall model will test each hypothesis. If the ages of the DV and DNV partners are significantly different, ANCOVAs will be conducted as age may further moderate the relationships tested in Aim 2. To test the hypothesis that emotional regulation during evocative partner stimuli will be reduced compared to regulation during neutral stimuli (**Hypothesis 2a**), we will test the 2 (evocative vs. neutral) x 2 (WATCH vs. DON'T REACT) interaction term, collapsing across partner type in the placebo condition. To test the hypothesis

that emotion regulation during evocative partner stimuli will be reduced by alcohol, (**Hypothesis 2b**) we will test the 2 (evocative vs. neutral) x 2 (WATCH vs. DON'T REACT) interaction term collapsing across partner type in the alcohol condition. To test the hypothesis that DV partners are less able to regulate emotion during evocative stimuli than the DNV partners (**Hypothesis 2c**), we will test the 2 (DV vs. DNV) x 2 (evocative vs. neutral) x 2 (WATCH vs. DON'T REACT) in the placebo condition. Finally, to test the hypothesis that alcohol interferes with the ability to regulate emotion for DV partners compared to DNV partners (**Hypothesis 2d**), we will test the 2 (DV vs. DNV) x 2 (alcohol vs. placebo) x 2 (evocative vs. neutral) x 2 (WATCH vs. DON'T REACT) interaction.

15) **Provisions to Monitor the Data to Ensure the Safety of Subjects**

1. The experienced and qualified professionals responsible for determining serious adverse events in the proposed study “Emotions and Decisions of Couples” will be the PI and co-Investigator for the study [name]. and [name]. [name] has experience with both oral and intravenous alcohol administration and will work with [name] to identify any adverse events.

Any serious adverse events that do occur during the course of the study will immediately be reported to the University of New Mexico Human Research Protections Office as an adverse event.

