3. On a yearly basis, the PIs will file a report to HRRC that contains all adverse events that occurred in the prior year. The study will be terminated should it be determined that study procedures resulted in violent arguments in three or more couples.
4. All female participants will be required to take a urine-based pregnancy test on any day in which they will participate in the experimental conditions (placebo and alcohol). If a participant tests positive for pregnancy, she will not be allowed to continue with the study and will be paid at a prorated rate.
5. The PI and collaborators for the study will always be present or on call while participants are undergoing administration of alcohol.
6. The study will involve administering alcohol to participants, and will be done in accordance with NIAAA guidelines for administering alcohol in human studies (www.niaaa.nih.gov/Resources/ResearchResources/job22.htm). All participants will be 21 years of age or older. Before administration participants will be notified of how much alcohol they will receive in terms of standard drinks and peak blood alcohol range in plain English, and will also be informed about the length of time required to participate in the study and for their blood alcohol levels to return to safe levels (<.03g%). Participants will be instructed not to drive to appointments. Once the experiment is completed, participants will be directed to a private assessment room that is near a bathroom that can be monitored easily by research associates. Participants will also be provided with snacks and water after participating. Before participants will be allowed to leave the CTSC laboratory, two consecutive breath alcohol concentration readings that are .03g% or below will be required. Finally, participants will be compensated with a gift card payment of \$40 after the placebo session and \$100 after the alcohol session. The alcohol session payments include the time during which the participant is decreasing to .03g%.
7. Referral to treatment: We are excluding participants who meet DSM-IV criteria for alcohol dependence based on an initial phone screen. If participants meet diagnostic criteria for alcohol dependence at the laboratory visit, however, they will be provided with an active referral consisting of a research staff contacting local treatment facilities if the participant so chooses. The study does not have a follow-up phase so we will not monitor increases in alcohol use over time.

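### Beverage order is counterbalanced by design, but neither ANOVA includes it and nothing says it is balanced within DV and within DNV: a loss of precision that is cheap to recover

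*Combined protocol and SAP*

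**What the plan says.** Section 3 (Objectives) states that "the selected partners will participate in a counter-balanced placebo session and alcohol administration session". Section 11 (Study Methods, Emotion-Regulation Sessions) repeats "counter-balanced alcohol and placebo conditions" and points to procedures further down. What follows there covers how the beverages are dosed, prepared and drunk; it gives no rule for assigning order. DV and DNV partners are yoked on sex and relationship satisfaction or distress, and a shared beverage order within the pair is not mentioned.

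Section 14 (Data Analysis Plan) gives the models. Aim 1: "We will conduct a 2 (beverage condition: alcohol vs. placebo) x 2 (stimulus: evocative vs. neutral) repeated measures ANOVA with a between-subjects factor", the between-subjects factor being partner type. Aim 2: "All hypotheses will be tested using a 2 (beverage condition: alcohol vs. placebo) x 2 (stimulus: evocative vs. neutral", with regulation condition as a third within-person factor and partner type again between subjects. Neither model has an order, session or sequence term. The only adjustment in the plan is for age, and only if the two partner types differ significantly on it.

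The sample size is 112 DV and 112 DNV couples, one partner from each taking part in the experiment. No power calculation, effect size, SD or order effect is given.

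**The concern.** Order is a factor that the design itself creates. When the analysis leaves it out, any difference between alcohol-first and alcohol-second participants on a tested contrast is counted as unexplained variation between people.

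Two things are at stake. The first is precision: the standard error is larger than it need be. The second is conditional. If the alcohol-first share differs between DV and DNV, part of an order effect on the contrast passes into the DV-DNV comparison, and the plan has neither an allocation rule nor a model term to prevent it.

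The hypotheses are not equally exposed.

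- **1a** is the alcohol-minus-placebo difference, so a plain shift between first and second session enters it directly. With equal numbers in each order overall, the shift averages out of the estimate but stays in the error.
- **1b** averages each person over both sessions, so a plain shift cancels.
- **1c** is affected only if the shift differs between evocative and neutral stimuli.
- **2a, 2b, 2c and 2d** are affected only if the shift differs by stimulus and regulation condition together. For 2a and 2c (placebo session only) and 2b (alcohol session only), order is a between-person factor.
- Conditional bias from unequal DV and DNV shares concerns **1c, 2c and 2d**.

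**Working it through.** The plan has no figure of its own to reproduce here, so the size is worked out under stated assumptions.

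**Inputs.** From the documents: n = 112 per partner type. Assumed: two-sided 5% test; contrast score with SD 1 within each order; shift of -d if alcohol is first and +d if it is second. The two orders therefore differ by 2d, and d = 0.5 means a full 1.0 SD gap, an upper end. The case is a DV-DNV comparison of an alcohol-minus-placebo contrast, as in 1c and 2d. The figures do not carry over to 1a, 2a, 2b or 2c.

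**Reference effect.** With order and order x partner type modelled, error df = 224 - 4 = 220 and SE = sqrt(2/112) = 0.1336. The effect with 80% power is 0.376 SD, so effect/SE = 0.376/0.1336 = 2.814. The critical value is 1.971.

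**Inflation when order is omitted.** The order shift adds d² to the variance, so the estimated SE grows by k = sqrt(1 + d²).

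**Balanced within each type.** The estimate itself does not move with order; only its estimated SE is too large. Type I error is 2Φ(-1.96k) and power is approximately Φ(2.814 - 1.971k). For d = 0.3: 2.814 - 1.971 × 1.044 = 0.756, giving 77.5%.

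**Unstratified, or balanced only overall.** The estimate now also varies with the chance split, so the larger SE is correct on average. Type I error averages about 5% and power is approximately Φ(2.814/k - 1.971). For d = 0.3: 2.814/1.044 - 1.971 = 0.724, giving 76.6%.

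| d (SD) | k | Type I, balanced | Power, balanced: formula (simulated) | Power, not balanced within type: formula (simulated) |
|---|---|---|---|---|
| 0.2 | 1.020 | 4.6% | 78.9% (78.9%) | 78.5% (78.3%) |
| 0.3 | 1.044 | 4.1% | 77.5% (77.4%) | 76.6% (76.4%) |
| 0.5 | 1.118 | 2.8% | 72.9% (72.8%) | 70.7% (71.3%) |

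The simulated values use 40,000 runs per case; the last column simulates unstratified assignment. Fixing 112/112 overall without stratifying by type gave 78.5%, 76.1% and 70.5%, which is the same picture. At d = 0.1, k = 1.005 and the loss is negligible. With order modelled, simulated power was 79% to 80% and type I error 4.7% to 5.3% under every assignment scheme.

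**Conditional bias.** If the alcohol-first shares are pDV and pDNV, the DV-DNV estimate shifts by 2d × (pDV - pDNV) in absolute size. Under simple randomisation the share difference has SD sqrt(2 × 0.25/112) = 0.067. A one-SD chance gap at d = 0.3 gives 2 × 0.3 × 0.067 = 0.04 SD, against the 0.376 SD reference effect.

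**The case against.** The strongest reply is that counterbalancing already controls order. That largely stands. If the term is meant to hold within each partner type, nothing is biased and the tests err on the cautious side. The text does not say that it holds within type, but it does not exclude it.

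It is also fair that no figure in the documents supports any particular shift, and that the assumed values apply to demanding contrasts. A plain session effect drops out of 1b, 1c and 2d, and the documents give no reason to expect an order effect that differs between the two regulation instructions. Only the 0.5 SD case produces a marked loss.

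A reader might infer more than the documents support, in three ways.

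- **That an order effect is to be expected.** Section 4 says that "repeated exposures to aversive dyadic interactions result in a progressive amplification of the arousal response", and section 11 says "Each stimulus will be presented twice". The first concerns relationships over time, not two laboratory visits. The second is repetition within one task, once per regulation condition, and is the same in both sessions. No section says that the same clips are reused across sessions. The statement in section 14 that "The arousal level of evocative stimuli is matched between alcohol and placebo sessions" is compatible with different, matched sets.
- **That the omission inflates false positives.** It does not: type I error is below 5% with balance within type and averages about 5% without it. Excess error arises only conditionally, given a realised imbalance and an order effect on that contrast.
- **That the safety text undoes the blinding.** Section 15 says "Before administration participants will be notified of how much alcohol they will receive in terms of standard drinks and peak blood alcohol range". This can be read as one notice about the study as a whole, which would not reveal the session's beverage. It is in any case a separate matter from order, and an order term would not address it.

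**Conclusion.** The point holds as a matter of efficiency and specification. Order is a design factor, its allocation rule is not given, and it is absent from both models. It is not shown that any planned test is invalid.

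The loss for a DV-DNV contrast of 1c or 2d type is about 1 to 2 percentage points of power at a 0.2 SD shift, 3 to 4 at 0.3 SD, and 7 to 9 at 0.5 SD, from a base of 80%. This rests on an assumed order effect in the contrast itself, a two-sided 5% test and all 112 per group analysed. If the true shift is 0.1 SD or less, nothing of practical weight is lost. The reason to act is that the remedy costs almost nothing and also removes the conditional exposure of 1c, 2c and 2d to an unequal split.

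**What to change.** State the order-assignment rule in section 11, such that each partner type has 56 alcohol-first and 56 placebo-first participants. One way is to give both members of a yoked pair the same order and allocate half of the pairs to each order. Sharing an order within pairs is not enough by itself: it equalises the DV and DNV shares but does not make them 50:50.

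In section 14, add order (alcohol first or second), with its interactions with the within-person factors and with partner type, to both ANOVAs. Test each hypothesis with equal weight on the two orders, so that an uneven realised split does not enter the contrast.

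The cost is one allocation rule and terms for a factor already known for every participant. On each contrast score, order and order x partner type use 2 of 222 error degrees of freedom. If there is no order effect, that is the only price.

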EEG, Psychophysiology and Pupillary Response Acquisition - EEG and psychophysiology data will be collected using the BrainVision actiCHamp 64-channel, DC amplifier, 24-bit resolution, biopotential system. EEG data will be recorded with filters set at 1 and 30Hz, digitized at a sampling rate of 512Hz and stored on a computer using the PyCorder software. EEG data will be recorded to collect a 5-minute baseline measurement prior to administration of alcohol or placebo beverage. After beverage administration data will be collected for the duration of the emotion-regulation task (see below). To reduce confounding results due to artifacts, EEG signals will be examined for contamination by muscle activity and eye movement. Fast Fourier Transformation (FFT) analysis will be applied to 6-10 second epoch samples (corresponding to the delivery of stimuli) allowing for 1-s pre- and post-stimuli artifact subtraction with the spectral graph ranging from 0 to 30Hz at 0.5Hz-resolution. FFTs will be performed using EEGLab software to calculate 1) Absolute power (AP; power density of each frequency band expressed in microvolts squared; mV^2/Hz); 2) Relative power (RP; proportional contribution of each band to the total power across 1 – 30Hz). AP and RP will be transformed into Fisher's z-scores for statistical analyses. Skin conductance (SC) will be collected using the BrainVision GSR module with leads placed on the left index finger and left middle finger. SC will be recorded to collect a 5-minute baseline (as with EEG) measurement and for the duration of the emotion-regulation task and time-locked to evocative stimuli. SC data will be subjected to detrending and transformed to Fisher's z-scores for statistical analysis. Respiration and HRV will be measured using an integrated BrainVision respiration belt, and an EKG in Lead II position. As with EEG, baseline measures will be collected, and time locked to evocative events. EKG data will be quantified as respiratory sinus arrhythmia (RSA) which is a unique measure of parasympathetic activity and self-regulatory ability. Respiration and HRV data will also be transformed to Fisher's z-scores for statistical analysis. Pupillary response data will be collected using the EyeLink 1000 system high speed camera by SR Research (see sample data). Corneal reflection will be recorded at 250 Hz. The left and right pupil diameter measures will be averaged offline and baseline measures (1 sec prior to trial onset) will be subtracted. The difference between the maximum diameter during the trial and the baseline diameter will be calculated and transformed to Fisher's z-scores for statistical analysis. E-prime will control the flow of the emotion regulation task and generate timestamps to denote conditions for which all biopotential data can be analyzed.

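### The planned ANOVAs state no term for the DV-DNV pairing, the beverage order or the 5-minute baseline; adding them is a cheap improvement of probably minor weight, and each gain rests on its own unknown.

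*Combined protocol and SAP*

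**What the plan says.** **Models.** Section 14, Data Analysis Plan, uses a "repeated measures ANOVA with a between-subjects factor (partner type: DV vs. DNV" for both aims. The within-person factors are beverage and stimulus, plus regulation condition in Aim 2. Age, conditionally and for Aim 2, is the only covariate with a rule in that plan.

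**Pairing.** Section 3 has each selected DV partner "yoked to a DNV partner of the same sex and a relationship satisfaction within a five-point range". Section 11 repeats it: "DV partners will be matched and yoked to a DNV partner of comparable distress".

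**Order.** Section 11 specifies "counter-balanced alcohol and placebo conditions". It does not say whether order is balanced within partner type.

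**Baseline.** Section 11 is explicit for EEG: "EEG data will be recorded to collect a 5-minute baseline measurement prior to administration of alcohol or placebo beverage". For skin conductance, "SC will be recorded to collect a 5-minute baseline (as with EEG) measurement". For respiration and HRV, "As with EEG, baseline measures will be collected, and time locked to evocative events". Pupil data are handled separately: "baseline measures (1 sec prior to trial onset) will be subtracted". The Emotion-Regulation Task text in Section 12 also describes five minutes of quiet sitting as a baseline, without placing it before or after the beverage.

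No model statement contains a pair, order or session, or 5-minute baseline term.

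**The concern.** The design spends effort on matching, counterbalancing and baseline recording, and the analysis then treats the 224 tested partners as two independent groups. If yoked partners resemble each other on the score being tested, the assumed error variance is wrong. It is too large for DV versus DNV tests (H1b, H1c, H2c, H2d) and, for inference beyond the sample, too small for tests collapsed over partner type (H1a, H2a, H2b). If responses shift between the first and second session, the shift sits in the error term. If the session's starting level predicts the later response, that variation stays in the error term for H1a. What is at stake is some power, and a modest departure from the nominal level in some tests.

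**Working it through.** **Inputs from the documents.** 112 DV and 112 DNV couples with one tested partner each (Sections 3 and 6), so 112 yoked pairs. There is no power calculation to reproduce: alpha, effect size, within-pair correlation, session effect and baseline correlation are not given.

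**Assumptions.** Two-sided 0.05; per-person contrast score with SD 1; complete pairs. The reference difference is the one with 80% power unpaired: (1.960 + 0.842) × √(2/112) = 0.374.

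**(a) Pairing.** Let ρ be the within-pair correlation of the contrast score.

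- Group tests: true variance is (1 − ρ) times the assumed one. True type I error = 2[1 − Φ(1.96/√(1 − ρ))].
- With 0.374/√(2/112) = 2.799, planned power = Φ((2.799 − 1.96)/√(1 − ρ)); power using the pair = Φ(2.799/√(1 − ρ) − 1.96).
- Collapsed tests, inference beyond the sample: true variance is (1 + ρ) times the assumed one. Type I error = 2[1 − Φ(1.96/√(1 + ρ))].
- If matching is the only link between pair members, ρ is about the share of contrast variance explained by sex and satisfaction, so their multiple correlation with the score must be √ρ.

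| ρ | √ρ | Group tests: type I error | Power, planned | Power, pair used | Gain (points) | Collapsed tests: type I error |
|---|---|---|---|---|---|---|
| 0.05 | 0.22 | 0.044 | 80.5% | 81.9% | 1.4 | 0.056 |
| 0.1 | 0.32 | 0.039 | 81.2% | 83.9% | 2.7 | 0.062 |
| 0.3 (upper illustration) | 0.55 | 0.019 | 84.2% | 91.7% | 7.5 | 0.086 |

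Simulation of 112 pairs agrees: 0.043, 0.039 and 0.019 for the group tests; 0.056, 0.060 and 0.086 for the collapsed tests. At ρ = 0 nothing is gained. A paired t-test then has 60.5% power against 60.8% unpaired at d = 0.30.

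**(b) Order.** Let h be the second-minus-first session shift in SD of the tested score.

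- H1a, H1c and H2d use the alcohol-minus-placebo difference, which moves by +h or −h according to order. With half the participants in each order, SE factor = √(1 + h²): 1.005 at h = 0.1 and 1.020 at h = 0.2.
- H2a to H2c are each tested within one beverage condition, so the score moves by ±h/2. SE factor = √(1 + h²/4): 1.001 and 1.005.
- H1b averages the two sessions and is unaffected.

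The shift must act on the contrast itself: an additive shift for H1a, session by stimulus for H1c, and session by stimulus by regulation for H2a to H2d.

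**(c) Baseline.** With r the correlation between the baseline difference and the alcohol-placebo difference, the residual variance factor is 1 − r²: 0.91 at r = 0.3 and 0.75 at r = 0.5. The SE falls by 4.6% and 13.4%. Subtracting a session baseline cancels exactly in every evocative-minus-neutral contrast, so the direct use is H1a. It covers EEG, skin conductance and respiration/HRV; slider ratings have no such baseline and pupil data are already corrected.

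**The case against.** The strongest case is that this is too small to matter. Much of it stands. Pairs are matched only on sex and satisfaction, and Section 5 already restricts every couple to a screening satisfaction score below 47, which limits what satisfaction can explain. The tested scores are within-person contrasts, in which stable differences between people cancel. So ρ may be near zero, and nothing in the documents supports 0.3.

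The remedy also has a cost. With a random pair effect whose variance is truncated at zero, simulated type I error for the group tests at ρ = 0 is about 0.053 to 0.055, where the planned test is exact. That limits which version of the remedy to use.

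The inflation of the collapsed tests depends on the target of inference. Conditional on the matching variables, the same tests are conservative (0.044 to 0.039 at ρ = 0.05 to 0.1), and Section 5 calls the participants a convenience sample.

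A reader might infer more than the documents support:

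- *The group comparisons are invalid.* With positive ρ they are conservative.
- *One unknown governs all three gains, or a pair term sharpens every test.* Only the pairing gain depends on ρ, and for the collapsed tests with positive ρ the pair term widens the standard error.
- *Omitting order biases the results.* It does not if order is balanced within partner type. The documents leave that open. As an illustration, 60% of DV and 50% of DNV partners taking alcohol second, with h = 0.2, would shift the H1c or H2d group difference by (0.6 − 0.4) × 0.2 = 0.04 SD.
- *No baseline is used, or all baselines precede the beverage.* The pupil measure subtracts one, and only the EEG text states the timing outright.

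**Conclusion.** The point holds as a cheap improvement, probably of minor weight. The models omit three features that the design itself provides, and the group comparisons remain usable without them. The pairing figures assume positive ρ, and I would rely on the 0.05 to 0.1 rows. The order cost stays within 2% of the standard error for shifts up to 0.2 SD. The baseline term may give the largest single gain, but for one hypothesis and some outcomes only, and subject to the timing of the recording. Every size here comes from an assumed range.

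**What to change.** Keep the planned contrasts and write the following into the Data Analysis Plan.

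1. For each hypothesis, compute one contrast score per participant and fit it on partner type and order, both coded ±0.5, with pair accounted for. Choose one of two forms in advance:
   - a within-pair analysis (fixed pair effect for H1b, H1c, H2c and H2d; pair means for H1a, H2a and H2b), which holds its level at ρ = 0; or
   - a random pair effect that keeps members of broken pairs and allows the pair variance to go negative.
2. For H1a on EEG, skin conductance and respiration/HRV, add the alcohol-minus-placebo baseline difference as a covariate, only where the baseline is confirmed to precede the beverage in both sessions.
3. State the population to which the collapsed tests are meant to apply.
4. State whether H1b and H1c use WATCH trials only; Section 14 attaches that restriction explicitly only to H1a.

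Cost: analysis wording, a few degrees of freedom, and under one power point if ρ is 0. No extra data or participants are needed. Truncating the pair variance at zero would add the slight excess in type I error described above, which is why the second form should allow negative values.
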